The primary objective of this study will be to test the feasibility and efficacy of a 3 month exercise physiologist consultation program. Specifically, our aims will be to:

- a. Test the feasibility of a 3-month exercise physiologist led program
- b. Measure the effect of an exercise physiologist collaboration and intradialytic exercise on the physical function of HD patients using the 30 second STS test,

handgrip strength test [required for frailty scale], 8-foot TUG test and patient physical activity based off of the Low Physical Activity Questionnaire.

3. Administrative Organization

The study will be administered from Satellite Healthcare, Inc., [name]. The study site will be Satellite Healthcare Milpitas. [name].

4. Study Design

a. Experimental design of the study

Randomized controlled trial (RCT) proof of concept study design

b. Study population

Convenience sample from prevalent HD patients from Satellite Milpitas Hemodialysis center in Northern California.

c. Sample size

n=50 (25 intervention - 25 control)

d. Study Outcomes

Feasibility outcomes

- Adherence calculated as the total number of self-reported exercise sessions attempted by the patient when EP not present divided by the total number of hemodialysis sessions. This information will be collected from the patient at the weekly meeting with the EPs.
- Adverse events defined as any injury, impairment or medical condition that was directly or suspected to be due to performing the prescribed exercise.

Efficacy Outcomes

- Change in physical function as measured by the 30 second sit to stand test (STS), handgrip strength test (HGST) and the 8 foot timed up and go test (TUG). Performed prior to initiation of dialysis at their mid-week dialysis session.

5. Study Procedures

a. Subject selection procedures

The Principal Investigator is responsible for screening subjects for the study, ensuring subjects meet all inclusion criteria.

b. Inclusion criteria

- Age 18 years or greater
- Ability to understand and communicate English
- Diagnosis of ESRD and currently undergoing in-center hemodialysis
- On HD for longer than 6 weeks
- Approved by the Satellite Milpitas Medical Director and/or referring physician

c. Exclusion criteria

- Previous major amputations
- Inability to independently ambulate
- Known to be pregnant

d. Recruitment procedures

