- A modified version of the Fried Frailty Index Score will be used to assess for the presence of frailty in both groups at the start of the study. The modification will be the replacement of the Minnesota Leisure Time Activity Questionnaire (MLTAQ) used to measure the low physical activity portion of the FFI with the Low Physical Activity Questionnaire

(LoPAQ). This was previously compared to the MLTAQ in a study of dialysis patients¹⁴.

- Exercise physiologist will encourage patients to complete their individualized exercise routines during their dialysis sessions for which the EP is not present but also at home at their convenience.
- Adverse events can be reported directly to the center manager or the PI. The EP will ask directly about adverse events at every meeting.

6. Data Analysis Plan

Demographic data: age, gender, ethnicity, weight, BMI, end stage kidney disease cause, co-morbid conditions, vintage on dialysis, dialysis treatment details and biochemical indices will be collected. Paired t-test or Wilcoxon-sign-rank will be used to compare the pre and post intervention STS, Hand Grip Test, TUG and modified FFI results depending on the distribution of the data. Patients who drop out or withdraw from the study will be included in the final outcomes with intention-to-treat analysis.

7. Timeline

Timeline (months)	1	2	3	4	5	6	7
Refine protocol							
Staff in-services							
Patient recruitment							
Exercise physiology intervention							
Evaluation interviews							
Data cleaning							
Data analysis							
Papers/Report write up							

IDEx Data Collection Plan

Test	Initial Assessment	Week 1	Week 2	Week 3	Week 4	Week 5	Week 6	Week 7	Week 8	Week 9	Week 10	Week 11	Week 12
Demographic 
 • Name/MR No. • DOB/Age • Gender • Racial Origin • Height • Smoker • Dialysis Vintage (months) • Renal Disease 	x												
Comorbidities 
 • Lung • PVD • Cerebral • Diabetes • Hypertension • Heart Failure 	x												
Dialysis Info 
 • Weight (dry) • BMI • KtV • Hb, PO4, K • Blood Pressure 	x												
Physical Function Tests 
 • Sit to Stand • Timed up and go • Hand Grip 	x											x	
Modified Fried Frailty Index	x											x	
EP Meeting Record	x	x	x	x	x	x	x	x	x	x	x	x	x

References

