Weight Loss If yes, give one point towards frailty.	Self-reported weight loss ≥ 10 lbs/year based off dry weight. (Yes or No)
Physical endurance/energy If No to #1 OR if every day/every week given as #2 give one point towards frailty.	
 1. Do you feel full of energy? (Yes or No?) 2. During the last month, how often have you rested in bed during the day? (every day, every week, not at all)
Low Physical Activity If no as an answer for very energetic physical activity OR moderately energetic physical activity give one point towards frailty.	Frequency of mildly energetic, moderately energetic and very energetic physical activity using LoPAQ (see attachment e)
Weakness If grip strength is below the 20% cutoff for gender and BMI listed, then give one point towards frailty.	
Hand grip strength in kg, dominant hand, average of 3 measurements
 
Frailty: cutoff point Grip strength lowest 20%
 
Men
 
BMI < 24: < 29 kg BMI 24-26: < 30 kg BMI 26-28: < 30 kg BMI > 28: < 32 kg
 
Women
 
BMI < 23: < 17 kg BMI 23-26: < 17.3 kg BMI 26-29: < 18 kg BMI > 29: < 21 kg

Slow Walking Speed If TUG test takes ≥ 19 seconds then give one point towards frailty.	Timed Up and Go ≥ 19 seconds
If total points towards frailty is ≥ 3 then patient meets criteria for frailty by Fried Frailty Index	

Reference: (Fried et al. Frailty in older adults: evidence for a phenotype. Journal of Gerontology. 2001;56:M146-156);

e. Low Physical Activity Questionnaire

Low Physical Activity Questionnaire (LoPAQ)

1. Please check all of the statements that describe your walking in the last week
 I walked around the neighborhood
I walked _____ times during the week.
I walked for approximately _____ minutes per session.
 I walked for transportation (i.e., to the store, etc.)
I walked _____ times during the week.
I walked approximately _____ minutes per session.
 I walked for the purpose of improving my fitness or for pleasure (above and beyond daily necessities)
I walked _____ times during the week.
I walked approximately _____ minutes per session.
 I did not walk.

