- Make a copy of the updated Exercise Plan form. Provide one to the patient and place one in the Patient Information binder.

3. Weekly visit #12

- Complete the POST-Study Assessment form for both control and intervention patients.
- Complete the Progress Note form.
- Scan the POST-Study Assessment form for all patients and email to [name] at [contact]

4. Reminders

- Report any adverse events (side effects from exercise) to the Center Manager and email [name] at [contact]
- At any point, a patient may choose to leave the study. If this happens, notify the Center Manager [name] and email to [name] at [contact]

Pre and Post Intervention Assessment

Hand Grip Strength Measurements: Using the Handgrip strength dynamometer take the best of three measurements for the non-fistula arm. If both arms have fistulas, use the arm that is not currently being accessed. If no fistula is present, use the non-dominant arm. Chart whether the left or right arm is used for the test. For the post-assessment make sure it is the same hand used in the pre-assessment. Pause 10-20 seconds between each test.

Handgrip Strength		
Test 1:	Test 2:	Test 3:
Average:		Hand Used:

Timed Up and GO (TUG): Record time in seconds for the patient to walk 8 feet in a straight line and return to a seated position. Patient is allowed one practice run. Two are counted. Note the average of the two. Chart if an assistance device such as a walker or cane is needed and note the type of assistance device.

Timed Up and Go (TUG) (seconds)	
Trial #1:	Trial #2:
Average:	Assistance Device:

Sit-to-Stand: Have the patient sit with arms crossed over the chest stand up and sit down as quickly as possible. Record the number of times they can go from sitting to standing in 30 seconds.

Sit-to-Stand (Repetitions/ Time)	
# of repetitions:	Repetitions/Time:

Low Physical Activity Questionnaire: Administer the questionnaire on the following page as instructed. Scan and email back results of this and the above physical function tests to [contact]. [see attachment e]

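### Section 6 promises intention-to-treat inclusion of leavers, but its paired tests cannot use a patient without a post value; unless leavers are tested or a value is supplied, the function analysis is complete-case

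*Combined protocol and SAP*

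**What the plan says.** **Promise.** Section 6 states: "Patients who drop out or withdraw from the study will be included in the final outcomes with intention-to-treat analysis". It names no method for doing so.

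**Tests.** The sentence before it reads: "Paired t-test or Wilcoxon-sign-rank will be used to compare the pre and post intervention STS, Hand Grip Test, TUG and modified FFI results", with the choice depending on the distribution. No other test is named.

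**Timing.** The data collection table shows the function tests and the frailty index at the initial assessment and in one late column. The EP Weekly Checklist (Attachment h) has progress notes and exercise plans at visits 1 to 11. At visit 12 it says: "Complete the POST-Study Assessment form for both control and intervention patients". So there is no interim function value.

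**Leavers.** The checklist reminders say: "At any point, a patient may choose to leave the study. If this happens, notify the Center Manager", followed by an email. No early-exit test, imputation rule, model or sensitivity analysis appears anywhere in the document.

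**Size.** Section 4c gives 25 patients per arm. No dropout rate is assumed, although the introduction lists high dropout among the barriers to exercise programmes in the United States.

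**The concern.** The promise goes beyond analysing patients in their assigned arm: it says that leavers will be in the final outcomes. A paired test works on the within-patient difference. A patient with no post value has no difference and drops out of the calculation without any decision being recorded.

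One missed final assessment removes sit-to-stand, grip, timed up-and-go, the activity questionnaire and the frailty index together, because they are all collected on that one occasion.

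At stake is whether the reported change describes everyone randomised or only those who stayed. If leavers fared worse than stayers, the remaining patients overstate the improvement and the paired test is significant too often. If leaving is unrelated to change, only precision is lost. If leavers fared better, the improvement is understated. Only one arm carries the burden of exercise, so both the amount of loss and its link to change could differ between arms.

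**Working it through.** The plan gives no power, effect size, SD or dropout figure, so there is nothing of its own to reproduce. The check has two parts.

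**1. Can the plan as written include a leaver?**
- Required: a pre and a post value for each patient (Section 6).
- Available: one baseline and one post value, with nothing between (data collection table; Attachment h).
- Obtaining the post value from a leaver: not expressly required. The listed step is notification.
- Replacing it if absent: no rule.

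A leaver who is not tested therefore contributes no pair. A patient who stops exercising but is tested at the end contributes normally. Adherence and adverse events need no post test.

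**2. How large could the effect be?** This is an illustration. The 25 per arm is from Section 4c; all else is assumed. Let d be the proportion missing and rho the correlation between a latent tendency to stay and a better change. The patients lowest on that tendency are missing.

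Shift in mean change among those remaining, in SD of change = rho × φ(z_d) / (1 − d), where φ is the standard normal density and z_d its d-quantile.

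At d = 20%, φ(z_d) = 0.280, and 0.280 / 0.80 = 0.350:

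| rho | −0.3 | 0 | 0.3 | 0.5 |
|---|---|---|---|---|
| Shift (SD) | −0.105 | 0 | 0.105 | 0.175 |

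At d = 10%, 0.1755 / 0.90 = 0.195, and the shifts are −0.058, 0, 0.058 and 0.097.

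Simulated chance of a significant improvement when the true change is zero (arms of 25, the lowest 3 or 5 missing, two-sided 5% level):

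| Missing | Test | rho −0.3 | 0 | 0.3 | 0.5 |
|---|---|---|---|---|---|
| 3 of 25 | paired t | 1.3% | 2.5% | 4.8% | 7.7% |
| 5 of 25 | paired t | 0.9% | 2.5% | 6.5% | 12.1% |
| 5 of 25 | signed-rank | 0.9% | 2.5% | 6.3% | 11.4% |

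Between arms, with 20% missing in each, the bias is the difference of the two shifts:
- rho 0.5 in both arms: 0.175 − 0.175 = 0.
- rho 0.5 against 0: 0.175 − 0 = 0.175 SD; false significant benefit about 8%.
- rho 0.5 against −0.3: 0.175 + 0.105 = 0.28 SD; about 14%.

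For scale, the standard error of one arm's mean change with 20 pairs is 1/√20 = 0.224 SD, and that of the between-arm difference is √(2/20) = 0.316 SD. In every case shown, the shift is below one standard error of its own estimate.

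**The case against.** **The plan may already intend to test everyone.** Visit 12 covers both arms, and the same step asks for the post forms of all patients to be sent in. This is a single unit that patients attend three times a week. Testing someone who has merely stopped exercising is a fair reading. This stands in part: it narrows the firm gap to patients who refuse testing, die or move away. But no line says that someone who has left the study is still tested, and the one instruction about leavers does not mention it. The consent pages are not in the text available, so any wording there cannot be judged.

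**An analyst could carry baseline forward.** That is possible, but nothing specifies it, and a rule chosen after the data are seen is not pre-specified.

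**The sizes are assumed.** This stands. Neither the dropout rate nor rho has a source in the documents, and the results run from harmful through zero to reversed. The gap between promise and method does not depend on them.

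**This is a 50-patient proof-of-concept study.** Feasibility is its first aim and is unaffected. Efficacy is nevertheless part of the stated primary objective, and a few leavers in 25 matter.

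Three stronger readings are tempting and not supported:
- That the plan excludes leavers. It does not say so; this is an inference from the tests.
- That the results will favour exercise. The documents give no direction.
- That the pre-post test suffers more than a between-arm comparison would. The between-arm figures above are as large when the link between leaving and change differs by arm.

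**Conclusion.** The point holds in conditional form. Section 6 makes a promise that its named tests cannot keep for any patient without a post value, and the plan neither expressly obtains nor supplies that value. Unless it does, the analysis of sit-to-stand, grip, timed up-and-go and the frailty index is complete-case.

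The size is unknown. The illustrative 0.11 to 0.18 SD shift and 7 to 12% false-positive rate (paired t) assume 5 of 25 missing, rho of 0.3 to 0.5 and a true change of zero. Equal dropout in the two arms does not by itself protect a between-arm comparison. The plan should be changed, but the fault does not undermine the feasibility results.

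**What to change.** 1. **Section 5.** State that stopping exercise is not leaving the study. Final sit-to-stand, grip, timed up-and-go, activity questionnaire and frailty index are sought from every randomised patient still dialysing at the unit who has not withdrawn consent to measurement.
2. **Section 6.** Name one method, fixed before data are seen, that uses patients with baseline only. Options are a baseline-constrained longitudinal model for sit-to-stand, grip and timed up-and-go, or multiple imputation by arm before the paired test. Report the numbers missing and the reasons by arm. A baseline-adjusted regression or ordinal model of the post value alone is not enough, because it drops the same patients as the paired test.
3. **Sensitivity.** Add one simple analysis that sets leavers' change worse than completers', because a method with only baseline to draw on cannot remove bias from dropout related to the outcome. A penalty of 0.5 SD with 20% missing lowers that arm's mean change by 0.2 × 0.5 = 0.10 SD; 1.0 SD lowers it by 0.20.
4. **Label.** If post values stay missing and are neither modelled nor imputed, call the result complete-case, not intention-to-treat.

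**Cost.** A few sentences, and a few extra final tests by existing staff in patients who already attend the unit. Patients who refuse, die or leave the unit stay missing, and the sensitivity penalty is a chosen value.

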6. For dialysis patients the non-fistula dialysis arm will be used. If both arms have a fistula, then the arm with the inactive fistula will be used. If no fistula is present, then the non-dominant arm will be used.

Reference: (Handgrip Strength Protocol. Tufts University Nutrition Collaborative, 2003)

c. 8 Foot Timed Up and Go

Equipment/set-up

Place a chair (approximately 17 inches in height) against a wall or firm object for safety to prevent it from sliding backwards. Place a cone on the floor exactly 8 ft away (distance measured is from the front edge of the chair to the back edge of the cone). Ensure a minimum of 4 ft of clearance beyond the cone to allow for turning room. A stopwatch is also required.

Starting Position

Patient is seated in the chair with hands on thighs and feet flat on the floor.

Protocol

Patient is instructed that on the signal “go,” they are to rise from the chair (pushing off of thighs or chair is permitted), walk “as quickly as possible” around the cone and return to a seated position in the chair. The participant is told that they will be timed and should therefore walk as quickly as possible but not to run. Following a demonstration, the patient is allowed one practice trial followed by two test trials.

Scoring

The clinician begins the timer when the “go” signal is given (even if the patient has not begun to move) and stops the time at the exact instant that the participant’s buttocks contacts the chair following the walk segment. Note the scores of both test trials to the 1/10th second yet the faster of the two times is recorded on the assessment form for evaluation purposes. Results obtained with this test may be compared to age-related normative values.

Adaptation

Use of an assistive device is permitted if required (remember to mark what type of device the patient used on the evaluation form) yet does not allow for comparison with age related, normative values from the Senior Fitness Test. Be sure to retest the patient using the same device on following visits. Additional trials can be administered without a device or a different type of device if appropriate.

Score > 8.5 seconds is associated with high fall-risk in community-dwelling older adults.

Reference: (Rose, Jones, & Lucchese, 2002)

d. Modified Fried Frailty Index (Frailty = ≥ 3 of the below criteria)

Fried Frailty Index V2.0	
Category	Criteria
Weight Loss If yes, give one point towards frailty.	Self-reported weight loss ≥ 10 lbs/year based off dry weight. (Yes or No)
Physical endurance/energy If No to #1 OR if every day/every week given as #2 give one point towards frailty.	
 1. Do you feel full of energy? (Yes or No?) 2. During the last month, how often have you rested in bed during the day? (every day, every week, not at all)
Low Physical Activity If no as an answer for very energetic physical activity OR moderately energetic physical activity give one point towards frailty.	Frequency of mildly energetic, moderately energetic and very energetic physical activity using LoPAQ (see attachment e)
Weakness If grip strength is below the 20% cutoff for gender and BMI listed, then give one point towards frailty.	
Hand grip strength in kg, dominant hand, average of 3 measurements
 
Frailty: cutoff point Grip strength lowest 20%
 
Men
 
BMI < 24: < 29 kg BMI 24-26: < 30 kg BMI 26-28: < 30 kg BMI > 28: < 32 kg
 
Women
 
BMI < 23: < 17 kg BMI 23-26: < 17.3 kg BMI 26-29: < 18 kg BMI > 29: < 21 kg

Slow Walking Speed If TUG test takes ≥ 19 seconds then give one point towards frailty.	Timed Up and Go ≥ 19 seconds
If total points towards frailty is ≥ 3 then patient meets criteria for frailty by Fried Frailty Index	

Reference: (Fried et al. Frailty in older adults: evidence for a phenotype. Journal of Gerontology. 2001;56:M146-156);

e. Low Physical Activity Questionnaire

Low Physical Activity Questionnaire (LoPAQ)

1. Please check all of the statements that describe your walking in the last week
 I walked around the neighborhood
I walked _____ times during the week.
I walked for approximately _____ minutes per session.
 I walked for transportation (i.e., to the store, etc.)
I walked _____ times during the week.
I walked approximately _____ minutes per session.
 I walked for the purpose of improving my fitness or for pleasure (above and beyond daily necessities)
I walked _____ times during the week.
I walked approximately _____ minutes per session.
 I did not walk.
2. In the past 7 days, did you participate in other activities that would be described as "light" activities? These are activities that make your heart beat a bit faster than usual—you could talk and sing while doing them. Examples would be: light yard or gardening work, bowling, golfing, boating (motor), leisure bicycling, stretching, yoga, chair exercises or light housework such as folding laundry or washing dishes?
 no yes
if yes, I participated in these light activities _____ times during the week for an average of _____ minutes per session.
3. In the past 7 days, did you participate in activities (other than walking) that would be described as "moderate" activities? These activities would make your heart beat faster than usual, and you could talk, but not sing while doing them. Examples of moderate activities would be: aerobics class, swimming (the side stroke or breast stroke), bicycling in the neighborhood, playing badminton or table tennis, softball, downhill skiing or moderate housework such as vacuuming or making beds.
 no yes
if yes, I participated in these moderate activities _____ times during the week for an average of _____ minutes per session.
4. In the past 7 days, did you participate in activities (other than walking) that would be described as "vigorous" activities? These would make your heart beat lots faster, make you breathe heavily, making your talking broken up by large breaths. Examples of vigorous activities would be: jogging or running, playing tennis or racquetball, playing soccer, basketball, cross-country skiing, using stepping machines or other equipment at the gym.
 no yes
if yes, I participated in these vigorous activities _____ times during the week for an average of _____ minutes per session.
5. In the past 7 days, did you do specific exercises for strengthening muscles?
 no yes
if yes, I participated in these strengthening exercises _____ times during the week.
6. In the past 7 days, did you do exercises for stretching your muscles (flexibility exercises)?
 no yes
if yes, I participated in these stretching or flexibility exercises _____ times during the week.
7. In terms of physical activity and walking, was this a typical week for you?
 no yes
8. In the past 7 days, how much time did you spend sitting, watching television, reading or in front of a computer?
_____ hours/day (average)
9. In the past 7 days, did you nap at home during the day?
 no yes
if yes, I napped _____ times.
when you nap, how long do you nap?
_____ minutes
10. In the past 7 days, how many hours were you in bed at night? _____ hours/night (average)

11. Do you work outside the home? no yes
if yes, does your job require you to do walking?
 no yes
if yes, your job require you to do physical exertion such as lifting?

(Johanson et al, Characterization of Physical Activity and sitting time among patients on Hemodialysis using a new physical activity instrument. Journal of Renal Nutrition 25:1, 2015 25-30)

f. EP Weekly Progress Note

How did the exercises go in the last week? At how many of your other sessions last week did you attempt to complete your exercises? How many of your aerobic exercises did you complete last week?

Have there been any noticeable changes that you have observed from our last meeting?

Is there anything that you are able to do now that you could not do before (endurance, strength, or flexibility)?

Have you experienced any symptoms or side effects from your exercise? If yes, what were they? (e.g., pain during any of the exercises? Any dizziness or light-headedness during or post-exercise?)

How can we modify the exercises from our last meeting?

Frequency	Intensity	Type	Time
-----------	-----------	------	------

What new exercises should we add or change for this upcoming week? (Document additional exercises for the new week and changes in prescription)

What are your exercise goals for the next week?

g. EP Exercise Plan

WARM UP						
ACTIVITY	SETS	REPS	TIME	DIST	INTENSITY**	NOTES

Aerobic Exercises		
Number of Attempts	Average Time	Average Distance

CORE BODY – STRENGTH TRAINING					
EXERCISES	SETS	REPS	WEIGHT/BANDS	REST TIME	NOTES

UPPER BODY – STRENGTH TRAINING					
EXERCISES	SETS	REPS	WEIGHT/BANDS	REST TIME	NOTES

LOWER BODY – STRENGTH TRAINING					
EXERCISES	SETS	REPS	WEIGHT/BANDS	REST TIME	NOTES

h. EP Weekly Checklist

INDEX VISIT CHECKLIST

1. Initial Intake visit

- Complete the PRE-Study Assessment form for both control and intervention patients.
- Provide intervention patient with an initial Exercise Plan form.
- Make a copy of the Exercise Plan form. Provide one to the patient and place one in the Patient Information binder.
- Scan the PRE-Assessment forms for all patients and email to [name] at [contact]

2. Weekly visit #1-11

- Complete the Progress Note form.
- If any alterations are made to the exercise plan, complete a new Exercise Plan form.
- Make a copy of the updated Exercise Plan form. Provide one to the patient and place one in the Patient Information binder.

3. Weekly visit #12

- Complete the POST-Study Assessment form for both control and intervention patients.
- Complete the Progress Note form.
- Scan the POST-Study Assessment form for all patients and email to [name] at [contact]

4. Reminders

- Report any adverse events (side effects from exercise) to the Center Manager and email [name] at [contact]
- At any point, a patient may choose to leave the study. If this happens, notify the Center Manager [name] and email to [name] at [contact]

Pre and Post Intervention Assessment

Hand Grip Strength Measurements: Using the Handgrip strength dynamometer take the best of three measurements for the non-fistula arm. If both arms have fistulas, use the arm that is not currently being accessed. If no fistula is present, use the non-dominant arm. Chart whether the left or right arm is used for the test. For the post-assessment make sure it is the same hand used in the pre-assessment. Pause 10-20 seconds between each test.

Handgrip Strength		
Test 1:	Test 2:	Test 3:
Average:		Hand Used:

Timed Up and GO (TUG): Record time in seconds for the patient to walk 8 feet in a straight line and return to a seated position. Patient is allowed one practice run. Two are counted. Note the average of the two. Chart if an assistance device such as a walker or cane is needed and note the type of assistance device.

Timed Up and Go (TUG) (seconds)	
Trial #1:	Trial #2:
Average:	Assistance Device:

Sit-to-Stand: Have the patient sit with arms crossed over the chest stand up and sit down as quickly as possible. Record the number of times they can go from sitting to standing in 30 seconds.

Sit-to-Stand (Repetitions/ Time)	
# of repetitions:	Repetitions/Time:

Low Physical Activity Questionnaire: Administer the questionnaire on the following page as instructed. Scan and email back results of this and the above physical function tests to [contact]. [see attachment e]

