- The Satellite Healthcare database will be used to identify all in-center hemodialysis patients at the Satellite Milpitas Dialysis Center
- This list of potential subjects will be approved by the Satellite Milpitas Medical Director who will screen to ensure they meet inclusion criteria.
- The study research associate (RA) and PI ([name]) will meet with the potential screened subjects in the dialysis center at the patient's weekly dialysis sessions
- The RA and PI will describe the study using a one-page information sheet and consent form as approved by the IRB.
- The RA and PI will offer the patient to take the information home and discuss with their relatives and significant others
- The RA and PI will then approach eligible participants again to consent to participate in the study. After consent is obtained, participants will be randomized into two groups using sequentially numbered opaque sealed envelopes.

e. Study Intervention

- 12 exercise physiologist consultations over 12 weeks
- Up to 3 exercise physiologists will implement an individualized resistance exercise program using elastic bands

f. Study Measures and Activities

- Subjects will meet with an exercise physiologist once weekly during one of their usual in-center HD sessions over a 3-month period.
- At the initial visit, the following physical function tests will be performed on the patient by EP: STS, HGST and TUG.
- At subsequent consultations, exercise physiologists will provide exercise plans and collect feedback on the exercises from the patients.
- EPs will tailor exercise routines to the individual patients based on a combined aerobic and resistance exercise program.

Aerobic Exercise

Participants will be asked to commence at a minimum of walking 3 times per week commencing at 20 minutes, and increasing both intensity and time up to 30 minutes x 3 times per week.

Resistance Exercise

Participants will be instructed to initially exercise various upper, core and lower body muscle groups using resistance bands for 1 set of 10 repetitions twice weekly. Intensity and repetitions of exercises will be adapted to participants' abilities throughout the 12 weeks. Warm up and warm down exercises will be included where relevant.

- Weekly progress notes and exercise checklists will be employed to monitor the types of exercises used. (see attachments f-h)
- The estimated duration for the appointments will be 30 minutes

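### The weight-loss item of the modified frailty index scores any loss of 10 lb or more in a year, whatever the intent, so deliberate loss can be misclassified as frailty (low priority)

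*Combined protocol and SAP*

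**What the plan says.** Attachment d (Modified Fried Frailty Index) defines the weight-loss criterion as "Self-reported weight loss ≥ 10 lbs/year based off dry weight. (Yes or No" and scores it with "If yes, give one point towards frailty". The reference to dry weight deals with fluid. It does not deal with intent. Weight loss is one of five criteria, and the classification rule is "If total points towards frailty is ≥ 3 then patient meets criteria for frailty by Fried Frailty Index".

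Section 5f describes a single change to the index: "The modification will be the replacement of the Minnesota Leisure Time Activity Questionnaire (MLTAQ") by the LoPAQ. It says nothing about the weight-loss criterion.

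The index is used twice. Section 5f says it is "used to assess for the presence of frailty in both groups at the start of the study". Section 6 then says that a paired t-test or Wilcoxon signed-rank test "will be used to compare the pre and post intervention STS, Hand Grip Test, TUG and modified FFI results". The IDEx Data Collection Plan marks the index at the initial assessment and once more near the end.

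On the intervention, section 5f says "EPs will tailor exercise routines to the individual patients based on a combined aerobic and resistance exercise program", and for the aerobic part "Participants will be asked to commence at a minimum of walking 3 times per week".

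**The concern.** The other four criteria in Attachment d (low energy, low activity, weak grip, slow walking) each describe a deficit. Weight loss that a patient chose is not a deficit, yet under the stated rule it earns the same point as wasting. The plan gives no reason for counting all loss alike.

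Two results could be affected. The first is the description of baseline frailty in both groups. The second is the paired comparison of the index in section 6, where a point gained or lost through deliberate loss is read as a change in frailty.

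The error could not be repaired afterwards from the planned data. The Pre and Post Intervention Assessment form has no field for weight loss or its reason, and the IDEx Data Collection Plan marks dry weight at the initial assessment only. If the reason is not asked at the visit, such points cannot be identified later.

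**Working it through.** The plan states no figure for this item, so there is none to reproduce. The check is of the scoring rule, followed by simple arithmetic.

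**Inputs from the documents**
- One point for loss of 10 lb or more in a year; five criteria; frail at 3 or more (Attachment d).
- Programme of 12 weeks (section 5e).
- 25 patients per arm (section 4c).

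**Assumptions, not in the documents**
- The item looks back over the 52 weeks before each assessment.
- POST falls 12 weeks after PRE.
- Between 5% and 15% of patients had a deliberate loss of 10 lb or more in the year before PRE. This range only shows scale.

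**Step 1. Effect on classification.** Let k be a patient's points on the other four criteria. A deliberate loss makes the total k + 1. The label changes only if k is below 3 and k + 1 is at least 3, that is, only if k = 2. Patients with k = 0 or 1 stay non-frail, and those with k = 3 or 4 are frail anyway.

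**Step 2. Possible scale at baseline.**
- 0.05 × 25 = 1.25 and 0.15 × 25 = 3.75, so about 1 to 4 patients per arm carry such a point.
- The arm mean rises by 1.25/25 = 0.05 to 3.75/25 = 0.15 points.
- The number reclassified as frail is smaller, because only those with k = 2 change label. The documents do not give that share.

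**Step 3. Effect on the paired change.** The two look-back windows share 52 − 12 = 40 weeks, and 40/52 = 77%. The effect depends on when the deliberate loss fell:

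| Timing of the deliberate loss | PRE point | POST point | Change |
|---|---|---|---|
| Reaches 10 lb within the 40 shared weeks | 1 | 1 | 0, cancels |
| Reaches 10 lb only by counting the first 12 weeks of the PRE window | 1 | 0 | −1, looks like improvement |
| Reaches 10 lb only by counting the 12 programme weeks | 0 | 1 | +1, looks like worsening |

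Points can therefore be lost as well as gained. Each net crossing moves an arm's mean change by 1/25 = 0.04 points. The documents give no standard deviation or target effect for the index against which to judge that.

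**Step 4. Could the programme alone trigger the item?** A loss made wholly within the programme would need to average 10/12 = 0.83 lb per week for all 12 weeks. A smaller loss would count only if added to loss already made in the preceding 40 weeks.

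**The case against.** A reader might infer that the error runs against the intervention, because only that arm is told to exercise and any resulting weight loss would be scored as new frailty. The documents do not support this. The study aims concern feasibility and physical function. No weight target or diet component is described, and the weekly progress note and exercise plan do not ask about weight. The rate needed within the programme is 0.83 lb per week, and most of the two look-back windows overlap. Loss early in the PRE window can drop out and look like improvement. The net sign is unknown.

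A second objection is that little depends on the index. Frailty is not an eligibility criterion in section 5 and has no stratification role. Section 4d lists the sit-to-stand, handgrip and timed up and go tests as efficacy outcomes, but not the index. Deliberate loss before enrolment should be balanced between arms on average by randomisation. All of this stands and lowers the priority. It does not make the item correct: balance between arms still leaves the frailty count wrong in each, and section 6 does test the index.

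A third objection is that the documents never say the item was meant for unintentional loss. That is true. The point therefore rests on the content of the other four criteria and on the absence of any stated reason for counting all loss, not on the cited source of the index.

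A fourth objection concerns the remedy. In an open trial, wording that excludes loss due to exercise would let intervention patients put true wasting down to the programme and answer No, which would favour that arm. This also stands, and the fix allows for it.

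**Conclusion.** The point holds in a limited form. As written, the item scores deliberate loss of 10 lb or more as frailty, and nothing in the plan limits it to unintentional loss or records the reason. The firm consequence is misclassified baseline frailty, which can occur in either arm, and added noise in an ancillary pre/post comparison.

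The size is not established. The figure of 1 to 4 patients per arm depends wholly on the assumed 5% to 15%. That few patients will cross 10 lb because of the programme is a judgement from the 12-week length and the required weekly rate; the documents do not state it. The cancellation of loss in the shared weeks assumes a one-year look-back and consistent recall at both assessments.

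The listed efficacy outcomes do not use the weight-loss item and are unaffected. Low priority.

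**What to change.** In Attachment d, reword the item to: 'Unintentional weight loss of 10 lb or more in the past year, based on dry weight (Yes or No)'. Add one line to the Pre and Post Intervention Assessment form recording any loss of that size and the patient's stated reason, completed at PRE and POST in both arms. Score the point only for unintentional loss. In section 6, add that the index will also be reported with every such loss scored, as a sensitivity check.

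The cost is one changed phrase, one more form line and one extra tabulation, with no added visit, test or staff. The remaining weakness is reliance on self-reported intent in an open trial. Reporting both scorings shows whether the answer depends on it. The change should be made before the first patient is assessed, because the reason for a loss is not otherwise collected.
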